#### 19.7. BASELINE VARIABLES

Baseline variables will be summarized for those subjects enrolled in this trial. Continuous variables will be presented as means, standard deviations, and sample size (N). Discrete variables will be presented as a percent along with the number of subjects displaying the characteristic and the total number of subjects. The types of baseline variables summarized will be demographics, medical history and lesion characteristics.

#### 19.8. STATISTICAL ANALYSIS

##### 19.8.1. PRIMARY SAFETY

The primary safety endpoint of MALE+POD at 30 days will be analyzed by constructing a one-sided upper 97.5% confidence interval using the exact binomial distribution. This upper bound will be compared to the performance goal of 12%. The hypotheses being tested are:

$$H_0 : P_{MALE+POD} \geq 12\%$$

$$H_a : P_{MALE+POD} < 12\%$$

where  $P_{MALE+POD}$  is the proportion of subjects experiencing a MALE+POD event within 30 days of the procedure. All subjects that meet the ITT definition are included in this analysis.

##### 19.8.2. PRIMARY EFFICACY

The primary efficacy endpoint of freedom from MALE at 6 months plus POD at 30 days will be analyzed using a one-sided, single group, Z-test comparing the observed proportion of subjects free of MALE and POD to the performance goal of 74%. The hypotheses are:

$$H_0 : P_{MALE\_6+POD} \leq 74\%$$

$$H_a : P_{MALE\_6+POD} > 74\%$$

where  $P_{\text{MALE}_{6+\text{POD}}}$  is the proportion of subjects free of MALE at 6 months + POD at 30 days. The p-value associated with the standard Z-test will be provided along with a one-sided 97.5% lower confidence bound on the point estimate observed. All subjects that meet the ITT definition are included in this analysis.

The Z-test that will be used for analysis is the continuity corrected Z under the estimated  $P_{\text{MALE}_{6+\text{POD}}}$ . That is:

$$Z = \frac{\hat{p} - P_0 + c}{\sqrt{\hat{p}(1 - \hat{p})/n}},$$

where  $\hat{p}$  is the estimate of  $P_{\text{MALE}_{6+\text{POD}}}$ ,  $P_0$  is the performance goal of 74% under the null hypothesis, and

$$c = \begin{cases} -\frac{1}{2n} & \text{if } \hat{p} > P_0 \\ \frac{1}{2n} & \text{if } \hat{p} < P_0 \\ 0 & \text{if } |\hat{p} - P_0| < \frac{1}{2n}. \end{cases}$$

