#### 19.6. SAMPLE SIZE

The sample size for the primary efficacy endpoint of freedom from MALE at 6 months plus POD at 30 days was calculated using a one-sided, single group, normal approximation test of a proportion (with continuity correction) against a performance goal. The performance goal for this endpoint is 74% developed based on the information reported in table VIIb and figure 2A of Conte (2009). From figure 2A, the estimated 6-month rate of freedom from MALE + POD in the infra-popliteal group is 80.5% with 95% confidence interval calculated to be (77%, 84%). Applying the recommended 3% margin to the lower bound of the confidence interval yields the 74% OPG. Assuming the observed freedom from MALE+POD is 84% and a one-sided Type I error rate of 0.025, a sample size of 186 subjects provides 90% power to detect this difference between observed freedom from MALE+POD and the performance goal of 74%.

The sample size for the primary safety endpoint of MALE+POD at 30 days was calculated using the exact binomial distribution. This is also a one-sided, single group test of a proportion against a performance goal. The performance goal for this endpoint was established at 12%. This performance goal was derived from the information reported in table VIIa of Conte (2009). In that table, MALE+POD was not reported, however MALE and 30-day death were reported separately. The sum of those two estimates (8.9%) was used for sample size calculation. Conte (2009) established performance goals for safety endpoints by constructing a 95% confidence interval and using the upper bound of that interval as the performance goal. With some algebraic manipulation, a similar 95% confidence interval was established for the 8.9% point estimate of 30day MALE+POD which resulted in an upper bound of 11.9%. Therefore 12% is used as the performance goal for this endpoint. Assuming an observed MALE+POD rate of 5%

 Joseph L. Mills, Sr, MD, [name], David G. Armstrong, DPM, MD, PhD, [name], [name], [name], MPH, and [name], on behalf of the Society for Vascular Surgery Lower Extremity Guidelines Committee, The Society for Vascular Surgery Lower Extremity Threatened Limb Classification System: Risk stratification based on Wound, Ischemia, and foot Infection (WIFI). J Vasc Surg. 2014; Volume 59, Issue 1, Pages 220–234.e2

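### The primary efficacy Z-test uses the estimated variance, so at the planned n = 186 its true one-sided type I error is 3.2%, not the stated 2.5%

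*Combined protocol and SAP*

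**What the plan says.** Section 19.6 sizes the primary efficacy endpoint with a "one-sided, single group, normal approximation test of a proportion (with continuity correction) against a performance goal". The goal is 74%, the assumed rate is 84%, and a "one-sided Type I error rate of 0.025, a sample size of 186 subjects provides 90% power". The section does not say which variance the formula used. It takes 186 as the effective sample size and enrols 232 to allow for about 20% loss.

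Section 19.8.2 then defines the analysis: "The Z-test that will be used for analysis is the continuity corrected Z under the estimated" proportion. The printed formula is Z = (p̂ − P0 + c)/√(p̂(1−p̂)/n), with c = −1/(2n) when p̂ exceeds P0. A one-sided 97.5% lower bound is to accompany it, with no method named.

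The other co-primary endpoint, 30-day safety, is handled differently. Section 19.8.1 analyses it by "constructing a one-sided upper 97.5% confidence interval using the exact binomial distribution", and Section 19.6 sizes it with the exact binomial too.

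Section 19.11 restricts the primary analysis to complete data, so the realised n need not be 186. Section 19.12 requires both primary endpoints for study success.

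**The concern.** A test of a proportion against a fixed goal holds its level when the standard error describes the data under the null hypothesis. Here the standard error comes from the observed proportion. Above one half, p(1−p) falls as p rises, so any p̂ above 74% gives a smaller standard error than the null value and a larger Z. The error always favours declaring success.

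Three things are at stake:

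- **The stated error rate.** Section 19.13 makes no alpha adjustment because both primary endpoints must be met. That argument requires each test to hold 0.025 on its own. If the device is clearly safe but efficacy is truly 74%, the chance of a false study success approaches the size of the efficacy test. The patency test is gated on the primaries and inherits the problem.
- **A contestable borderline result.** At some observed counts the plan would declare the goal exceeded while an exact lower bound, of the kind used for safety, sits below it.
- **Consistency.** The sample size and the analysis appear to use different variances, and the documents give no reason for it.

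**Working it through.** **Inputs.** P0 = 0.74, P1 = 0.84, one-sided α = 0.025 (z = 1.960), power 90% (z = 1.2816), planned n = 186, enrolment 232 (Section 19.6); the Z formula (Section 19.8.2).

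**1. Reproduce the plan's 186.** With the null variance under H0:

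n = [(1.960·√(0.74·0.26) + 1.2816·√(0.84·0.16)) / 0.10]² = [(1.960·0.4386 + 1.2816·0.3666)/0.10]² = 13.295² = 176.8.

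The continuity correction, (n/4)·(1 + √(1 + 2/(n·0.10)))², gives 186.6, in line with the stated 186. Approximate power at n = 186 is 89.9%.

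With the estimated-variance denominator that Section 19.8.2 specifies:

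n = [(1.960 + 1.2816)·0.3666/0.10]² = 141.2, or 151.1 after the same correction. This does not reproduce 186.

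**2. Find the planned test's cut-off at n = 186.** The correction is 1/(2·186) = 0.00269.

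- 149 successes: p̂ = 0.8011, numerator 0.8011 − 0.74 − 0.0027 = 0.0584, standard error √(0.8011·0.1989/186) = 0.02927, Z = 1.995. Success.
- 148 successes: Z = 1.793. Failure.

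The null standard error is √(0.74·0.26/186) = 0.03216. With it, 149 successes give Z = 1.815, a failure, and 150 give Z = 1.983, a success.

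**3. Exact error and power at n = 186**, as binomial tails:

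| Test | Cut-off | P(success given 74%) | P(success given 84%) |
|---|---|---|---|
| As planned (estimated variance, corrected) | 149 | 0.0321 | 0.936 |
| Null variance, corrected | 150 | 0.0213 | 0.909 |
| Exact binomial | 150 | 0.0213 | 0.909 |

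The Clopper-Pearson one-sided 97.5% lower bound at 149/186 is 73.6%. At 150/186 it is 74.2%.

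**4. Other sample sizes.** The same steps were repeated for every n from 180 to 232.

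- Planned test: size above 0.025 at 41 of 53 values (77%), mean 0.0279, minimum 0.0229 (n = 194), maximum 0.0341 (n = 181). At full enrolment, n = 232, it is 0.0253.
- At those 41 values the planned cut-off is one success below the exact cut-off. At the other 12 the two are the same.
- Null-variance corrected Z: size never above 0.0226, but one success stricter than the exact test at 13 of the 53 values. At n = 185 it needs 150 and has power 0.880, while the exact test needs 149 and has power 0.914.

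**5. Role of the continuity correction.** At n = 186 it does not move the planned cut-off, which is 149 with or without it. At n = 185 it does: 149 with the correction (size 0.0234), 148 without (0.0351). It therefore offsets the inflation at some sample sizes and not at others.

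**The case against.** The strongest reply is that this is ordinary normal-approximation error and is small. The planned and exact cut-offs never differ by more than one subject over n = 180 to 232. At n = 186 the dispute is over the single outcome 149/186, which has probability 1.1% if the true rate is 74% and 2.7% if it is 84%, and the exact bound there misses the goal by only 0.4 points. The plan openly calls its method a normal approximation, so 0.025 can be read as nominal. The 3.2% also belongs to one value of n: the size is 2.34% at n = 185 and 2.32% at n = 220.

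The dependence on n stands, which is why the range is given above. It does not rescue the test: the number of complete cases cannot be chosen, the average is above 2.5%, and about three-quarters of plausible sample sizes exceed it. The one-subject difference also stands, but on a pass/fail decision one subject can settle the outcome.

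It is also fair to say that the sizing mismatch costs no power (93.6% at n = 186, against the stated 90%) and that the null variance in Section 19.6 is inferred from reproducing 186. The mismatch is a point about consistency, not the source of the excess error.

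Finally, study success also needs the exact safety test, and Section 19.10 substitutes a random-effects comparison if sites differ. Neither brings this Z-test back to 0.025.

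**Conclusion.** Wrong as written. At the planned 186 evaluable subjects, the test in Section 19.8.2 has an exact one-sided type I error of 3.21% against the stated 2.5%, about 28% higher in relative terms (0.0321/0.025 = 1.28). Over n = 180 to 232 the rate is 2.3% to 3.4%, averaging 2.8%. The cause is the variance term: replacing only p̂(1−p̂) with P0(1−P0) at n = 186 moves the cut-off from 149 to 150 and the error to 2.13%.

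The calculation assumes independent subjects with a common success probability of 74%, a pooled analysis, and a critical value of 1.960. It should be corrected because it affects a primary decision rule, the error favours success, and the correction is nearly free.

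**What to change.** In Section 19.8.2, replace the Z-test with an exact binomial test of the 74% goal, and declare success when the Clopper-Pearson one-sided 97.5% lower bound exceeds 74%. This matches Section 19.8.1 and gives the lower bound a stated method that agrees with the test. Section 19.6 should then state the variance behind 186 and report the exact power.

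Putting P0(1−P0)/n in the denominator would also control the error and would match the sizing formula. It is the second choice, because it is stricter than the exact test at some sample sizes (power 0.880 at n = 185).

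The cost is wording only, with no added subjects. At n = 186 the threshold rises from 149 to 150 and power at 84% falls from 93.6% to 90.9%, still above the stated 90%. Because of discreteness, exact power can dip slightly below 90% at nearby n: at n = 188 the cut-off is 152 and P(X ≥ 152 given 84%) = 0.897. The change should be made before outcome data are seen; made after a borderline result, it would look data-driven.

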### 19.8.3. SECONDARY EFFICACY ENDPOINTS

The secondary efficacy endpoint of 6-month patency will be estimated as the proportion of tacked segments of the lesion(s) that are still patent at 6 months. A one-sided lower 97.5% confidence bound will be calculated for this estimate using the standard normal approximation. This lower bound will be compared to the performance goal of 64%. The hypotheses being tested are:

$$H_0 : P_{\text{Patency}_{6\text{month}}} \leq 64\%$$

$$H_a : P_{\text{Patency}_{6\text{month}}} > 64\%$$

where  $P_{\text{Patency}_{6\text{month}}}$  is the proportion of subjects whose tacked portion of the vessel is still patent 6 months post procedure. Patency will also be displayed using a Kaplan-Meier curve.

The secondary efficacy endpoint of target limb salvage at 6 months will be summarized using the Kaplan-Meier method to estimate freedom from above-ankle target limb amputation. The final 6-month estimate will be presented along with 95% confidence intervals. All subjects that meet the ITT definition are included in this analysis.

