#### 7.4.2. ANGIOGRAPHIC INCLUSION CRITERIA

Subjects must meet all the following Angiographic Inclusion Criteria. The response for each criterion below must be “Yes”:

1. Reference vessel diameter is between 1.5 mm and 4.5 mm, inclusive (by visual estimate)
2. Only one limb requires treatment during the Index Procedure

**Note:** If the subject has bilateral BTK disease, the Investigator should choose the limb that most closely meets eligibility criteria. If the chosen limb does not meet final eligibility after PTA treatment, the subject should not be enrolled at that time. This subject may be brought back for potential study device treatment to the contralateral limb per the protocol requirements. Only one limb may receive study device treatment.

3. Ability to cross study device(s) antegrade through target lesion
4. Has de novo or restenotic target lesion(s) with pre-PTA stenosis of  $\geq 70\%$  or is occluded (by visual estimate) and is indicated for PTA treatment with a standard balloon catheter

**Note:** Diseased segments with  $>30$  mm of healthy vessel between them are considered separate target lesions

**Note:** If any part of the lesion is restenotic, no part of the lesion should have more than 1 prior failure (by plain balloon angioplasty only), which must have occurred greater than 1 year (360 days) prior to the index procedure

**Note:** After PTA treatment, the target lesion is defined as the entire contiguous arterial segment length treated with angioplasty

5. Target lesion(s) located in the mid popliteal (P2), distal popliteal (P3), tibioperoneal trunk, peroneal, anterior tibial, or posterior tibial arteries

**Note:** The mid popliteal artery (P2) begins at the superior aspect of the patella. The most distal location of the tibial and/or peroneal artery(ies) ends at the beginning of the dorsalis pedis artery (DP). Tacks may not be implanted within 1 cm above the radiographic tibiotalar joint.

6. Target vessel(s) reconstitute(s) at or above the ankle or displays normal terminal branching

- If the target vessel is the peroneal artery, the artery must display normal terminal branching.
- If the target vessel is the anterior tibial (AT) artery or the posterior tibial (PT) artery, the artery(ies) must display reconstitution at least 1 cm proximal to the radiographic tibiotalar joint line, and continue into an intact runoff vessel (AT/dorsalis pedis or PT/plantar artery).

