### 19.4. SECONDARY ENDPOINTS

- Target lesion(s) tacked segment(s) patency at 6 months defined as the presence of blood flow using duplex ultrasound. If angiography is available within the 6-month follow-up visit window, it should be used in place of the duplex ultrasound. Evidence of no blood flow within the Tacked segment indicates restenosis/loss of patency.
- Target Limb Salvage defined as freedom from any above-ankle target limb amputation at 6 months.

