and a one-sided Type I error rate of 2.5%, a sample size of 171 subjects provides 90% power to demonstrate that the observed 30-day MALE+POD rate is below the performance goal of 12%.

Since the required sample size for the primary efficacy endpoint (186), is larger than the required sample size for the primary safety endpoint (171), an effective sample size of 186 subjects meeting the ITT definition will be assumed. Assuming approximately 20% loss to follow-up, total enrollment will be  $186/0.80$  or 232 subjects.

The secondary endpoint of primary patency of the tacked segment of the treated lesion at 6 months will also be formally tested against a performance goal of 64%. The performance goal of 64% was chosen as a result of a meta-analysis combining 13 papers that reported 6-month patency for standard PTA or from which the 6-month patency rate could be derived. These papers covered several patient populations, however all these populations are target populations for use of the Tack. A meta-analysis was performed on the results reported in these papers and the random effects estimate of 6-month patency was 63.5%. Therefore, 64% was chosen as the performance goal. Assuming an observed 6-month patency rate of 81% and a one-sided Type I error rate of 2.5%, the effective sample size given above for the primary efficacy endpoint of 175 would provide greater than 90% power to detect the difference between an observed 6-month patency of 81% and the performance goal of 64%.

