#### 19.13. MULTIPLICITY

There is no correction to alpha in controlling type I error for the primary endpoints as both endpoints must be met in order to declare study success. Additionally, the type I error will be controlled by testing the secondary endpoint hierarchically. That is, the secondary endpoint of 6-month patency will be formally tested if and only if the primary study endpoints are met. If the 6-month patency endpoint is met then the two-sided 95% confidence interval for the secondary endpoint of target limb salvage at 6 months will be reported. There is no formal hypothesis for this endpoint. There are no additional formal hypothesis tests and thus no further adjustments are necessary.

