Serious Adverse Event (SAE)	
A serious adverse event (SAE) is defined an adverse event that:
 
 
▪ led to death
 
▪ led to a serious deterioration in the health of the subject, that either resulted in: 
 
▪ a life-threatening illness or injury, or
 
▪ resulted in a permanent impairment of a body structure or a body function, or
 
▪ required in-patient hospitalization or prolongation of existing hospitalization, or
 
▪ resulted in medical or surgical intervention to prevent life-threatening illness or injury or permanent impairment to body structure or a body function, or
 
▪ led to fetal distress, fetal death or a congenital abnormality or birth defect.
 
 
 
 
Note: Planned hospitalization for a pre-existing condition, or a procedure required by the investigational plan without serious deterioration in health, is not considered a serious adverse event.

Standard Balloon Angioplasty	A standard balloon catheter (non-drug-coated) used to perform percutaneous transluminal (balloon) angioplasty. Also referred to as Plain Old Balloon Angioplasty (POBA)
Stroke	A neurological deficit lasting more than 24 hours with a brain imaging study (if performed) showing infarction or hemorrhage.
Study Device Procedure Start/End Time	
Start: The time the first Tack Endovascular System is advanced through the introducer sheath
 
End: The time of withdrawal of last post-Tack PTA balloon catheter

Term	Definition
Tacked Segment	Defined as the Tack device and 5 mm of artery proximal and distal to each Tack. If Tacks are within 10 mm of each other, they will be considered as a single tacked segment for the purposes of this patency assessment.
Target Lesion Tacked Segment Patency	Patency defined as the presence of blood flow using duplex ultrasound. If angiography is available within the follow-up visit window, it should be used in place of the duplex ultrasound. Evidence of no blood flow within the Tacked segment indicates restenosis/loss of patency.

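### Section 19.8.3 computes 6-month patency over tacked segments but states the tested hypothesis over subjects, with no rule for subjects who have several segments

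*Combined protocol and SAP*

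**What the plan says.** The mismatch lies within Section 19.8.3. The estimate "will be estimated as the proportion of tacked segments of the lesion(s) that are still patent at 6 months", and the lower bound, by the standard normal approximation, is placed on that estimate and compared with 64%. The parameter in the hypotheses, however, "is the proportion of subjects whose tacked portion of the vessel is still patent 6 months post procedure".

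The plan foresees several segments in one subject:

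- Section 7.4.2 allows more than one target lesion: diseased segments with more than 30 mm "of healthy vessel between them are considered separate target lesions".
- Section 24 merges neighbouring implants only when they are close: "If Tacks are within 10 mm of each other, they will be considered as a single tacked segment". Tacks further apart form separate segments, even within one lesion.
- Section 19.4 names the endpoint with optional plurals for both lesion and segment, but words failure in the singular: "Evidence of no blood flow within the Tacked segment indicates restenosis/loss of patency".

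Section 19.6 counts subjects ("an effective sample size of 186 subjects meeting the ITT definition will be assumed") and assumes 81% patency against the 64% goal. It does not say whether either percentage is per subject, limb, lesion or segment. Section 19.13 makes patency the one secondary test in the hierarchy: "the type I error will be controlled by testing the secondary endpoint hierarchically".

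**The concern.** Segments and subjects are different denominators and, where subjects have several segments, different quantities. Two things follow.

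First, a subject with one open and one occluded segment has no defined result. On the subject scale that subject could be a success or a failure. On the segment scale the subject contributes one of each and counts twice.

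Second, segments in one leg share inflow, runoff and patient factors, so they are likely to be correlated. A normal-approximation bound that treats them as independent is too narrow when subjects contribute several.

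The test follows the two primary endpoints and could support a claim. If the unit and the rule are still open when the data arrive, the choice could be made with the results in view.

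**Working it through.** **1. The plan's own figure.** Inputs from Section 19.6: goal 64%, assumed rate 81%, one-sided alpha 0.025, n = 175 (the same section also gives 186). With one independent unit per subject:

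power = Φ{[(0.81 − 0.64) − 1.96·√(0.64·0.36/n)] / √(0.81·0.19/n)}

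This gives 99.96% at n = 175 and 99.98% at n = 186. The stated figure of more than 90% reproduces; about 73 units would give 90%.

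**2. Subject-level test with the planned bound.** Reject if p̂ − 1.96·√(p̂(1 − p̂)/n) > 0.64. At n = 186 the pass mark is 132: 132/186 = 0.7097, lower bound 0.644, while 131/186 gives 0.639. Exact binomial size at 64% is 2.71%, and power is 99.97% at 81%. At n = 175 the pass mark is 124 and the size 3.36%. For 175 to 230 independent units the size of this rule lies between 2.5% and 3.5%. That is the baseline for the next step.

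**3. Segment-level test as written.** The number of segments per subject and the ICC are assumptions. Beta-binomial simulation with 186 subjects, true patency 64%, 40,000 trials per cell, and segments distributed as 1 + Poisson(mean − 1) except in the last row. The bound uses the total number of segments as n.

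| Segments per subject | ICC 0.1 | ICC 0.3 | ICC 0.5 | ICC 0.7 |
|---|---|---|---|---|
| mean 1.03 | 3.1% | 3.3% | 3.2% | 3.6% |
| mean 1.2 | 3.1% | 3.6% | 4.1% | 4.6% |
| mean 1.5 | 3.5% | 4.7% | 5.8% | 6.9% |
| mean 2.0 | 3.8% | 5.8% | 7.5% | 9.3% |
| exactly two | 3.5% | 5.0% | 6.2% | 7.5% |

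The Monte Carlo standard error is at most about 0.15 points (√(0.093·0.907/40,000)). As a rough check, two segments at ICC 0.5 have design effect 1 + (2 − 1)·0.5 = 1.5, and 1 − Φ(1.96/√1.5) = 5.5% before the baseline excess of the bound. A cluster-robust bound has size 2.8% to 3.3% in the same settings.

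**4. Why the combining rule matters.** Suppose 81% is per segment and each subject has two segments with correlation ρ. Then P(both patent) = 0.81² + ρ·0.81·0.19, which is 70.2% at ρ = 0.3 and 77.9% at ρ = 0.8. P(at least one patent) = 1 − (0.19² + ρ·0.81·0.19), which is 91.8% and 84.1%. The two rules describe different endpoints.

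**5. Power of an every-segment rule** (pass mark 132 of 186). If 81% is per subject, power stays at 99.97%. If 81% is per segment, power for ICC 0.1 / 0.3 / 0.5 / 0.7 is:

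- mean 1.2 segments: 99.3 / 99.6 / 99.8 / 99.9%
- mean 1.5 segments: 88.1 / 95.3 / 98.5 / 99.6%
- mean 2.0 segments: 28.0 / 63.2 / 88.8 / 98.1%

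**The case against.** The best defence is that the formal parameter is stated per subject, that the tacked portion of the vessel can be read as a collective term, and that the failure wording in Sections 19.4 and 24 points to any no-flow segment being a failure. The sample size is in subjects, and the pilot's 80.6% per patient (Section 4.2) is close to the assumed 81%. On that reading one loose sentence needs correcting. This is a fair guide to the likely intent, and the fix below adopts it. It does not remove the problem: the sentence that says what will be computed names segments, and the rule for mixed subjects is nowhere written. The pilot also defined patency differently, so the match with 81% is suggestive only.

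Three stronger readings are not supported.

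- *A reader might infer that the error control in Section 19.13 fails.* The testing order is intact. Any excess is a variance problem within one test, and it arises only if segments are the unit.
- *A reader might infer that the two units will usually disagree.* A conflicting dataset can be built: 186 subjects, 37 with two segments (223 in all), and 60 occlusions in 60 different subjects. Segments give 163/223 = 73.1%, lower bound 67.3%, a pass; subjects give 126/186 = 67.7%, lower bound 61.0%, a fail. But it contains no doubly occluded subject. With q = 60/223, independence predicts 37·q² = 2.7 such subjects and 128.7 successes. ICC 0.5 predicts 37·(q² + 0.5·q(1 − q)) = 6.3 and 132.3 successes, which meets the pass mark. At 81% per segment and a mean of 1.2 segments the units disagree in under 1% of simulated trials.
- *A reader might infer that the 64% goal is on the wrong unit.* The unit depends on 13 papers that the plan does not itemise. The literature review in Section 4.1 shows that units differ (6-month patency 35.1% to 91% per limb or lesion, 65% to 76% per patient), which justifies asking for confirmation and no more.

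The pilot does not settle how common multiple segments are. Its 33 tacked lesions in 32 subjects count lesions, and its mean of 2.8 Tacks (range 1 to 12 per lesion) counts implants.

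**Conclusion.** The point stands and should be fixed. As written, the bound in Section 19.8.3 is computed on a different unit from the hypothesis it is meant to test, and nothing in the plan links the two. That conclusion needs no assumption about clustering.

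The numerical consequence does, and it may be small. With few segments per subject or low ICC, the size is the ordinary 2.5% to 3.5% of this bound. It exceeds about 5.5% only at a mean of 1.5 segments with ICC 0.5 or more, or at about two segments with ICC of 0.3 to 0.5 or more, and reaches about 9% at the extreme of the range examined. If the test is run on subjects there is no clustering excess, but the result still depends on an unwritten rule.

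Both primary endpoints, the definition of study success, the hierarchical order and the stated power of more than 90% are unaffected.

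**What to change.** In Section 19.8.3:

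- Define the estimate as the proportion of subjects, in line with the stated hypothesis and the subject-based sample size.
- Pre-specify that a subject is patent only if every evaluable tacked segment shows flow, and that any segment without flow makes the subject a failure. This follows the failure wording of Sections 19.4 and 24.
- State how a subject with a non-diagnostic or missing segment is classified when the other segments show flow.
- State how ITT subjects without a Tack are handled. They leave after 30 days (Section 13.3.1), so Section 19.11 would probably exclude them, but an every-segment rule is otherwise met vacuously.
- Test this proportion against 64%, and report segment-level patency with a cluster-robust interval as supportive.

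In Section 19.6, state the unit of the 64% goal and of the 81% assumption and confirm that they match.

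The cost is SAP wording; no new data are needed. The downside is that an every-segment rule can lower the observed rate. Power stays above 99.9% if 81% is per subject, but could fall materially if it is per segment and many subjects have several segments. The unit of the 81% should therefore be confirmed when the rule is fixed, before endpoint data are available.
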